## 9.6. Relationship of an Adverse Events (AEs) to OCS Liver System

The investigator will assess the relationship of the Adverse Event (AE) to the OCS Liver System. The relationship will be assessed using the following categories:

- **Definitely Related:** There is a reasonable causal and temporal relationship between preservation with the OCS Liver System and the adverse event.
- **Probably Related:** It is more likely than not that there is a reasonable causal relationship between preservation with the OCS Liver System and the adverse event.
- **Unlikely Related:** There is a temporal relationship with preservation with the OCS Liver System and the adverse event, but there is not a reasonable causal relationship between the trial device and the event.
- **Unrelated:** There is no relationship between preservation with the OCS Liver System and the adverse event.

## 9.7. Severity

The investigator will rate the severity of the adverse event using the following categories:

- **Mild:** The adverse event is transient and/or easily tolerated by the subject.
- **Moderate:** The adverse event causes the subject discomfort and interrupts the subject's usual activities.
- **Severe:** The adverse event causes considerable interference with the subject's usual activities.

## 9.8. Pre-Existing Conditions

Pre-existing diseases or conditions will not be reported as adverse events.

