## 5.4. Safety Endpoint

Safety will be analyzed principally by examination of the frequency of liver graft-related serious adverse events (LGRSAEs) up to the 30-day follow-up after transplantation. This endpoint is defined as the average number of LGRSAEs through the 30 days post-liver transplantation per subject, consisting of the following serious adverse events (at most one per type per person):

- Primary non-function (defined as irreversible graft dysfunction requiring emergency liver re-transplantation or death with the first 10 days, in the absence of immunologic or surgical causes)
- Ischemic biliary complications (ischemic biliary strictures, and non-anastomotic bile duct leaks)
- Vascular complications (liver graft-related coagulopathy, hepatic artery stenosis, hepatic artery thrombosis and portal vein thrombosis)
- Liver allograft infections (liver abscess, cholangitis, etc.).

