### 7.2. Recipient Day of Transplant Assessment

The purpose is to conduct a final assessment of whether the potential consented recipient still meets the eligibility criteria. The following information will be verified and recorded on the day of transplant:

- **Eligibility:** Investigator will review and confirm that the potential consented recipient continues to meet all inclusion criteria and no exclusion criteria.
- **Demographics/Characteristics:**

- Date of birth or Age
- Gender, body mass index
- Race and Ethnicity
- Blood type and RH factor
- Recipient Model for End-stage Liver Disease (MELD) Score
- Recipient ID
- **Baseline Liver Function Tests:**
  - Bilirubin levels
  - Aspartate aminotransferase (AST)
  - Alanine aminotransferase (ALT)
  - Gamma-glutamyl transpeptidase (GGT)
  - Alkaline phosphatase
  - International normalized ratio (INR)
  - Serum Lactate level
- **Recipient Risk Factors & Medical History:**
  - Indication for transplantation: The primary etiology of Liver failure will be recorded
  - History of Hepatitis C
  - History of liver cancer
  - History of diabetes.

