## **9. EVALUATION OF ADVERSE EVENTS**

### **9.1. Evaluation of Liver Graft-Related Adverse Events (LGRAEs)**

Liver Graft-Related Adverse Events (LGRAEs) are those which have any untoward effect on the health or safety of the patient and that are related to the transplanted liver function (except for acute rejection). LGRAEs will be collected from the time a subject is transplanted with a liver preserved on OCS until the completion of the 30-day follow-up evaluation. A LGRAE will be followed until resolution or stabilization of the event.

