### 10.4. Analysis of Safety

Safety will be analyzed principally by examination of the frequency of liver graft-related serious adverse events (SAEs) up to the 30-day follow-up after transplantation. This endpoint is defined as the average number of liver graft-related serious adverse events through the 30 days post-liver transplantation per subject, consisting of the following serious adverse events (at most one per type per person):

- Primary non-function (defined as irreversible graft dysfunction requiring emergency liver re-transplantation or death within the first 10 days, in the absence of immunologic or surgical causes)
- Ischemic biliary complications (ischemic biliary strictures, and non-anastomotic bile duct leaks)
- Vascular complications (liver graft-related coagulopathy, hepatic artery stenosis, hepatic artery thrombosis and portal vein thrombosis)
- Liver allograft infections (liver abscess, cholangitis, etc.).

In addition, the numbers and percentages of subjects experiencing at least one liver graft-related AE, at least one (definitely or probably-related) device-related AE, at least one unanticipated AE, and at least one serious AE, and the number and percentage of deaths will all

be tabulated. Also, the number of liver graft-related adverse events and the number and percentage of subjects experiencing liver graft-related adverse events will be tabulated by system organ class and preferred term using MedDRA. A similar analysis will be performed for LGRSAEs. AEs will also be tabulated at the event level by system organ class and preferred term and the relationship of the adverse event to the device using counts and percentages. Similar analyses will be performed by the severity of the adverse event.

For livers that are not transplanted, the reason(s) for non-transplantation (including device failure) will be summarized using counts and percentages. The number and percentage of donor livers in the Donor Liver Population for which these was a device failure will also be presented.

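### Section 9.8 keeps pre-existing conditions out of adverse event reporting with no exception for worsening, which biases the serious-AE tabulation low and leaves the status of continuing coagulopathy unclear

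*Combined protocol and SAP*

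**What the plan says.** Section 9.8 is a single sentence: "Pre-existing diseases or conditions will not be reported as adverse events". It does not define what counts as pre-existing and does not mention worsening, new seriousness or recurrence.

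The principal safety endpoint is built from reported serious adverse events. Section 5.4 states: "This endpoint is defined as the average number of LGRSAEs through the 30 days post-liver transplantation per subject", counted "at most one per type per person". There are four types: primary non-function, ischemic biliary complications, vascular complications and allograft infections. In section 10.4 the vascular type reads: "Vascular complications (liver graft-related coagulopathy, hepatic artery stenosis, hepatic artery thrombosis and portal vein thrombosis". In section 5.4 the infection type reads: "Liver allograft infections (liver abscess, cholangitis, etc".

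Section 9.1 limits liver graft-related adverse events to those "that are related to the transplanted liver function (except for acute rejection", and starts the clock at transplant: "LGRAEs will be collected from the time a subject is transplanted with a liver preserved on OCS".

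Section 10.4 also tabulates the number and percentage of subjects with at least one serious adverse event. That row is not restricted to graft-related events, and section 9.5 asks sites to report any serious adverse event to the sponsor.

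**The concern.** Recipients come to transplant with end-stage liver disease. Several conditions that section 9.3 lists as anticipated adverse events, including renal dysfunction, ascites, pleural effusion, hepatic coma and coagulopathy, may already be present on the day of surgery. The usual convention is that a pre-existing condition is not an adverse event unless it gets worse. Section 9.8 gives the first half of that convention without the second.

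A site that follows the sentence literally has grounds not to report a serious deterioration of something the recipient already had, and another site may report it. Under-reporting can only lower the safety counts, and in a single-arm study there is no concurrent control group in which the same loss would show.

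**Working it through.** No figure in the plan bears on this rule, so the check is mainly a comparison of sections.

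1. **Is reporting restored elsewhere?** Section 9.1 defines graft-related events and names one exception, acute rejection. Section 9.2 defines seriousness, 9.3 and 9.4 deal with anticipated and unanticipated events, 9.5 covers recording, 9.6 relationship and 9.7 severity. Section 10.4 lists the tabulations. None says what to do when a pre-transplant condition worsens. Section 9.8 therefore stands unqualified.

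2. **Conditions not specific to the graft.** The exclusions in 6.2.2 remove fulminant liver failure, chronic hemodialysis and chronic renal failure (creatinine above 3 mg/dl for more than 2 weeks). They do not remove lesser renal dysfunction or ascites. Worsening of these conditions is not covered by 9.1 unless it is tied to graft function, so 9.8 decides. The affected output is the at-least-one-serious-AE row in 10.4.

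3. **Coagulopathy.** INR is a baseline test in 7.2, and 9.5 asks for a date of onset for every event. Coagulopathy that runs on from before transplant and becomes serious because the graft works poorly may have no distinct onset. Section 10.4 would count it as graft-related; 9.8 can be read as removing it. The text does not settle which governs. By contrast, the primary effectiveness endpoint in 5.1 counts INR of 1.6 or more on day 7 whatever the baseline value.

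4. **Portal vein thrombosis.** A recurrence after transplant in a recipient with a prior thrombosis could be called pre-existing, but the natural reading is that a clot forming after transplant is new. The ambiguity is weaker here.

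5. **Graft infections and new graft thromboses.** The allograft was not in the recipient before transplant, so an infection of it cannot pre-date transplant. Sections 9.1 and 9.5 require graft-related events from transplant onward to be captured, and 9.3 names cholangitis and portal vein thrombosis as post-transplant adverse events. These are reportable as the plan stands.

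6. **Illustrative arithmetic (assumed rates).** Let f be the share of recipients with a relevant prior condition and r the rate of serious worsening among them, with none reported. Both are assumptions: f from 5% to 30%, r from 5% to 20%. N = 184 is the maximum enrollment.
   - Events lost = 184 × f × r.
   - Low: 184 × 0.05 × 0.05 = 0.46. Middle: 184 × 0.20 × 0.10 = 3.68. High: 184 × 0.30 × 0.20 = 11.04.
   - Fall in events per subject = f × r = 0.0025, 0.02 and 0.06.

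   For the LGRSAE mean these are ceilings under the assumed rates. Coagulopathy and portal vein thrombosis belong to the same type, so at most one of the four possible counts per subject is at stake, and a lost event changes nothing if another vascular event is counted. For the at-least-one-serious-AE row, the same f × r gives a fall of at most 0.25 to 6 percentage points. A lost event matters there only if the subject has no other reported serious adverse event.

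**The case against.** The strongest reply is that 9.8 cannot do much harm to the principal endpoint. Its components are worded as graft-related or allograft events, 9.1 names acute rejection as the only exception, and 9.5 requires all graft-related events to be captured. Something new in the graft is not pre-existing. This stands for infections and for new thromboses. A reader might infer from 9.8 that the endpoint will miss cholangitis or graft thrombosis in anyone with such a history; the documents do not support that. The reply does not settle continuing coagulopathy, and it does not reach events that are not graft-specific.

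A second reply is that omissions could be found. Sections 14.1, 14.3 and 15.3 require case histories, source documents and monitoring of adverse event reports, and 15.8 provides an independent Clinical Events Committee. This partly stands. It would go too far to say that losses cannot be detected, even though the listed history in 7.2 ("Indication for transplantation: The primary etiology of Liver failure will be recorded", plus hepatitis C, liver cancer and diabetes) omits prior portal vein thrombosis and ascites. But a monitor checking against the protocol would find that a site applying 9.8 had complied, and the committee's charter is not in the documents.

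A third reply is that Appendix 2 schedules only graft-related adverse events, so other serious events may never reach the database. If so, the serious-AE row is already narrower than its label and 9.8 removes less from it. The effect on that row rests on the request in 9.5 for any serious adverse event.

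Finally, the safety analysis is descriptive and no test is affected. That stands, and it limits the consequence.

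**Conclusion.** The point holds in a limited form and should be corrected. Section 9.8 is a stated rule without an exception, not merely a missing detail. Applied literally, it biases low the tabulation of subjects with at least one serious adverse event, provided that row draws on all serious events as 9.5 implies. For the LGRSAE endpoint the finding is an ambiguity, clearest for serious graft-related coagulopathy continuing from before transplant and weaker for recurrent portal vein thrombosis. It is not a demonstrated gap.

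The direction is downward. The size cannot be estimated from the documents. The range of about 0.5 to 11 events in 184 only shows how the loss scales with assumed rates and complete non-reporting.

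A reader might also infer that the bias is concentrated in recipients with MELD above 30, or in those most prone to these events. The plan defines that subgroup only for the effectiveness endpoints (10.3.4 and 10.3.5), schedules no safety subgroups in 10.4, and gives no figure on which recipients are most affected.

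**What to change.** Amend section 9.8, and the eCRF completion guidance to match, so that it says three things:

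- A disease or condition present before transplant is not an adverse event if it is unchanged after transplant.
- It is reported if it worsens in severity or frequency, or if it newly meets a seriousness criterion in 9.2 because of that worsening. The link to worsening is needed: without it, an unchanged condition that merely prolongs the hospital stay would become reportable.
- Any event of the four types in 5.4 and 10.4 that arises in the transplanted liver is reported and counted whatever the recipient's history.

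The cost is a short text change, a few more event reports and possibly slightly less favourable safety counts. No analysis method and no treatment changes.

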## **10. STATISTICAL METHODS**

### **10.1. General**

Continuous variables will be summarized using descriptive statistics, specifically the mean, median, standard deviation, minimum, and maximum. Categorical variables will be summarized using frequencies and percentages.

All statistical procedures will be performed using SAS Version 9.3 or higher.

### **10.2. Analysis Populations**

#### **10.2.1. Per Protocol Population**

The Per Protocol (PP) Population will consist of all subjects who are transplanted and have no major protocol violations and for whom the donor liver received the complete preservation procedure. The major protocol violations that will exclude a subject from this population are the following:

- Ineligible for the study according to the recipient inclusion and exclusion criteria
- Ineligible for the study according to the donor organ inclusion and exclusion criteria
- Failure to complete adequate post-transplant assessments to support the primary, secondary or safety endpoints
- Other major protocol violations.

The primary analysis of effectiveness and of secondary and other endpoints will be based on the PP Population.

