### 4.1. Type of Trial

A prospective, multi-center, single arm Continued Access Protocol.

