## 5. TRIAL ENDPOINTS

### 5.1. Primary Effectiveness Endpoint

Incidence of Early Liver Allograft Dysfunction (EAD) or primary non-function, defined as presence of one or more of the following criteria:

- AST level  $> 2000$  IU/ml within the first 7 postoperative days;
- Bilirubin  $\geq 10$  mg/dl on postoperative day 7;
- INR  $\geq 1.6$  on postoperative day 7; or

- Primary non-functioning graft within the first 7 days (defined as irreversible graft dysfunction requiring emergency liver re-transplantation or death, in the absence of immunologic or surgical causes).

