#### **10.2.2. Modified Intent-to-Treat Population**

The Modified Intent-to-Treat Population (mITT) will consist of all subjects who are transplanted. The mITT analyses will be considered secondary analyses of effectiveness. The safety analysis will also be based on the mITT population.

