### **10.3.4. Primary Effectiveness Endpoint**

The primary effectiveness endpoint for this study is the incidence of Early Liver Allograft Dysfunction (EAD) or primary non-function, defined as presentation of one or more of the following criteria:

- AST level > 2000 IU/ml within the first 7 postoperative days;
- Bilirubin  $\geq$  10 mg/dl on postoperative day 7;
- INR  $\geq$  1.6 on postoperative day 7; or
- Primary non-functioning graft within the first 7 days.

This endpoint will be analyzed using the Per Protocol and mITT Populations. The Per Protocol analysis will be considered the primary analysis.

Subgroup analyses of the primary effectiveness endpoint will be performed for the following subgroups of patients:

- DCD (donation after circulatory death) patients
- Fatty liver patients
- Donor Age
- Recipient with MELD  $>$  30.

No data imputation or statistical tests will be performed for these subgroup analyses.

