## 10.5. Sample Size Determination

The sample size for this CAP was determined based on the rate of enrollment in the PROTECT trial. The maximum number of patients enrolled is 184.

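### The primary EAD rate of a single-arm study is taken on the Per Protocol set, so it is conditional on completed preservation and on an open list of violations; the planned mITT analysis should be primary

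*Combined protocol and SAP*

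**What the plan says.** Section 4.1 describes "A prospective, multi-center, single arm Continued Access Protocol". The primary endpoint (Section 5.1) is "Incidence of Early Liver Allograft Dysfunction (EAD) or primary non-function, defined as presence of one or more of the following criteria", with criteria covering the first 7 postoperative days.

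Section 10.2.1 limits PP to transplanted subjects without major violations and "for whom the donor liver received the complete preservation procedure". Its exclusion list names recipient ineligibility, donor ineligibility and inadequate post-transplant assessments, and ends with "Other major protocol violations". Neither a complete preservation nor the last category is defined. Section 10.3.2 has major deviations identified before database lock, partly by review of data listings, and its examples are expressly not exhaustive.

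For the primary endpoint, Section 10.3.4 says: "The Per Protocol analysis will be considered the primary analysis". Section 10.3.5 gives PP the same status for the secondary endpoints. The mITT population (Section 10.2.2) "will consist of all subjects who are transplanted"; it is secondary for effectiveness but is the set used for safety. Section 10.4 reports device failures in the Donor Liver Population and the reasons why livers were not transplanted.

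**The concern.** The objective in Section 4 is how effectively the device preserves and assesses donor livers. Whether preservation was completed is known only after treatment has begun, and it is itself part of how the device and its users performed. Conditioning the primary estimate on it removes some of the cases in which preservation went badly.

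The usual reason for a PP primary analysis is caution in a non-inferiority comparison. That reason is absent here: there is no control arm, margin or test. Nor is there a second arm subject to the same selection, so any distortion falls directly on the reported rate.

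The open violation category adds a second route. Each recipient's 7-day outcome is known long before lock, and no section requires exclusions to be decided without sight of it. At stake are the headline EAD/PNF rate and the primary figures for survival at Day 30 and at initial discharge.

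**Working it through.** **The plan's own figures.** None can be reproduced for this point. Section 10.5 states that "The sample size for this CAP was determined based on the rate of enrollment in the PROTECT trial" and that "The maximum number of patients enrolled is 184". It gives no expected EAD rate, performance goal, alpha, power or expected share of incomplete preservation.

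**Inputs.**
- From the documents: N = 184 transplanted recipients, the maximum.
- Assumed: PP EAD rate p = 15-25%; share excluded from PP 2%, 5% or 10%, so k = 4, 9 or 18 of 184; EAD rate r among the excluded, from r = p up to r = 100%.

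**Formula.** mITT rate = [p(N − k) + rk] / N. The shift from PP to mITT is therefore (k/N)(r − p).

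**Results for p of about 20%, in whole subjects.**

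| k | PP | mITT, r = p | mITT, r = 50% | mITT, r = 100% |
|---|---|---|---|---|
| 4 | 36/180 = 20.0% | 37/184 = 20.1% | 38/184 = 20.7% | 40/184 = 21.7% |
| 9 | 35/175 = 20.0% | 37/184 = 20.1% | 39/184 = 21.2% | 44/184 = 23.9% |
| 18 | 33/166 = 19.9% | 37/184 = 20.1% | 42/184 = 22.8% | 51/184 = 27.7% |

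At k = 18 and r = 100%, p of about 15% gives 25/166 = 15.1% against 43/184 = 23.4% (+8.3 points). With p of about 25% the figures are 42/166 = 25.3% against 60/184 = 32.6% (+7.3 points). Where r = p the shift is zero apart from rounding to whole subjects (at most 0.3 points either way).

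**Against sampling error.** The exact 95% interval for 37/184 is 14.6-26.6%, a half-width of (26.6 − 14.6)/2 = 6.0 points. In the middle case (k = 9, r = 50%) the intervals are 14.3-26.7% for PP and 15.5-27.8% for mITT, which overlap heavily. In the extreme case (k = 18, r = 100%) they are 14.1-26.8% and 21.4-34.8%. At p = 20% and k = 18, a shift above 6 points needs r − p > 0.06/(18/184) = 0.61, so r above about 81%. At k = 9 the largest shift is 3.9 points. Only the extreme scenarios exceed sampling error, but a selection bias, unlike sampling error, does not shrink as subjects are added.

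**Sign.** If excluded subjects did better than PP subjects, the shift would reverse. At r = 0, p = 25% and k = 18 it is (18/184)(0 − 0.25) = −2.4 points.

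**The case against.** Much is already in place. The same endpoint is analysed on mITT, safety uses mITT, deviations are listed and summarised by type, and device failures and reasons for non-transplantation are reported. No success criterion hangs on the word primary. A formal SAP is promised before data lock (Sections 10.3 and 10.6) and could close the open category. All of this stands and limits the harm, but the declared primary result is still the selected one.

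Three stronger readings are tempting and go beyond the text.

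- A reader might infer that the PP rate is certainly too low. The documents give no outcome data for excluded subjects, and those removed for ineligibility or inadequate assessments could differ in either direction.
- A reader might infer that PP strips out every device failure. A malfunction that did not interrupt preservation stays in PP, and Section 11.1 recognises staff error as well as malfunction. That section also says that a subject whose donor liver is damaged in this way waits for another, so incompletely preserved livers that are nevertheless transplanted may be few.
- A reader might infer that exclusions will be made with outcomes in view. The plan is silent on this; it does not say so.

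It is also tempting to count every liver started on OCS but not transplanted as a failure in a new composite endpoint. Section 1.2 presents judging suitability before transplant as an intended function of the device, so a turn-down is not plainly a failure.

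**Conclusion.** The concern holds in a limited form. The primary EAD/PNF rate, and the primary analysis of the secondary recipient endpoints, are conditional on completed preservation and on the absence of violations that are not fully listed. With no comparator or test, PP brings no compensating conservatism. The bias is likely, but not shown, to favour the device. On the assumptions above (2-10% of 184 excluded, PP EAD 15-25%, excluded subjects' EAD rate between the PP rate and 100%) the shift is about 0 to 8 points, with a middle case of 1.2 points. The effect is on the estimate and how it is read; type I error is not involved.

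mITT does not remove all conditioning. Livers started on OCS and never transplanted are outside both recipient sets.

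**What to change.** - Make mITT (all transplanted) the primary analysis set for the primary endpoint and for the two survival endpoints, with PP supportive. This also leaves the multiple imputation planned for missing primary values with subjects to act on; PP may exclude many of them for inadequate assessments.
- Define in Section 10.2.1 what counts as complete preservation, and replace the open category with a closed list.
- State that PP exclusions are judged without sight of post-transplant outcome.
- Show the Donor Liver Population counts already planned (livers started on OCS, device failures, livers not transplanted and why) beside the EAD rate. No new endpoint is needed.

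The cost is protocol and SAP wording. Both analyses are already planned and no additional data are needed, though someone shielded from outcomes must review the exclusions. The downside is that the headline rate may be slightly less favourable. This is a cheap improvement.

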Follow-up	
Patients will be followed for 24 months from the date of transplantation (some of which will be post-market).
 
The following data will be collected at 6 and 12 months:
 
 
Patient and graft survival
 
Liver graft-related SAEs (6 months only)
 
Liver graft-related re-hospitalization after initial discharge, and, if yes, the primary reason/diagnosis for the hospitalization and the length of stay
 
Information will also be collected on any diagnosis of ischemic biliary complications and, if so, the method of diagnosis and treatment.
 
 
The following data will be collected at 24 months:
 
 
Patient and graft survival.
 
Results of standard clinical practice or for cause liver biopsy will be collected (if applicable).
 

Analysis Populations	
 
The Per Protocol (PP) Population will consist of all subjects who are transplanted and have no major protocol violations and for whom the donor liver received the complete preservation procedure. The
 

	
primary analysis of effectiveness and of secondary and other endpoints will be based on the PP Population.
 

• The Modified Intent-to-Treat Population (mITT) will consist of all subjects who are transplanted. The mITT analyses will be considered secondary analyses of effectiveness.

• The Donor Liver Population will consist of all donor livers which have preservation initiated using the OCS Liver System.

Effectiveness Analysis	
The primary endpoint will be analyzed using the Per Protocol and mITT Populations. The Per Protocol analysis will be considered the primary analysis. Multiple imputation methods will be used for data imputation for any patients with missing values for this endpoint.
 
Each secondary effectiveness endpoint will be summarized using counts and percentages and an exact 95% confidence interval for the true percentage based on the binomial distribution. The secondary effectiveness endpoints will be analyzed using the PP and the mITT Populations. The Per Protocol analysis will be considered the primary analysis.

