## 5.2. Secondary Effectiveness and OCS Donor Liver Assessment Endpoints

- OCS donor liver assessment during perfusion, defined as, among donor livers preserved using OCS for the entire preservation period, the proportion of livers on which measurements of all of the following during perfusion will be available on OCS device before transplant:
  - Lactate level (every two hours)
  - Average bile production rate (based on total bile production volume and duration of OCS perfusion)
  - Hepatic artery pressure (continuously)
  - Portal vein pressure (continuously)
- Patient survival at Day 30 post-transplantation
- Patient survival at initial hospital discharge post liver transplantation.

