### 10.3.5. Secondary Effectiveness and OCS Donor Liver Assessment Endpoints

The secondary effectiveness endpoints for this trial are as follows:

- OCS donor liver assessment during perfusion, defined as, among donor livers preserved using OCS for the entire preservation period, the proportion of livers on which measurements of all of the following during perfusion will be available on OCS device before transplant
  - Lactate level (every two hours)
  - Average bile production rate (based on total bile production volume and duration of OCS perfusion)
  - Hepatic artery pressure (continuously)
  - Portal vein pressure (continuously)
- OCS Measurements during organ perfusion
- Patient survival at Day-30 post-transplantation
- Patient survival at time of initial hospital discharge post-transplantation.

These endpoints will be analyzed using the Per Protocol and mITT Populations, with the Per Protocol analysis being considered the primary analysis. Multiple imputation methods will be used for data imputation for patients with missing values for these endpoints.

Subgroup analyses of the secondary endpoints will be performed for the same subgroups of patients as for the primary effectiveness endpoint. No data imputation or statistical tests will be performed for these subgroup analyses.

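### The Per Protocol completeness exclusion is not tied to the endpoint analysed, so gaps in secondary or safety data can remove subjects whose EAD status is already known from the primary EAD analysis

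*Combined protocol and SAP*

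**What the plan says.** Section 10.2.1 lists the major protocol violations that take a subject out of the PP population. The third is "Failure to complete adequate post-transplant assessments to support the primary, secondary or safety endpoints". The three kinds of endpoint are joined by *or*, and the consequence is removal from the population, not from the analysis of one endpoint. *Adequate* is not defined.

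The same section makes PP the primary set for effectiveness. Section 10.3.4 repeats this for EAD: "The Per Protocol analysis will be considered the primary analysis". The mITT population holds every transplanted subject, but section 10.2.2 says "The mITT analyses will be considered secondary analyses of effectiveness". It adds: "The safety analysis will also be based on the mITT population".

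On missing data, the synopsis says of the primary endpoint: "Multiple imputation methods will be used for data imputation for any patients with missing values for this endpoint". Section 10.3.5 says of the secondary endpoints: "Multiple imputation methods will be used for data imputation for patients with missing values for these endpoints". Section 10.3.4 mentions imputation only for subgroups: "No data imputation or statistical tests will be performed for these subgroup analyses". Sections 10.3 and 10.6 leave further detail to a statistical analysis plan to be finalized before data lock.

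**The concern.** EAD is a one-week endpoint. Day-30 survival and the 30-day count of liver graft-related serious adverse events are settled later, and discharge survival can be. A completeness rule covering all of them lets later data decide who enters the estimate of an earlier outcome. The headline EAD rate would then depend on information that plays no part in defining EAD.

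The primary-endpoint part raises a second question. A subject with a missing EAD component could be excluded from PP under 10.2.1, or kept in PP and imputed under the synopsis. The plan does not say which.

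At stake is the reported PP effectiveness estimate. The protocol states no hypothesis test, performance goal or power, and section 10.5 sets the maximum of 184 from the PROTECT enrollment rate, so no formal decision rule is affected.

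**Working it through.** **Step 1: when each endpoint is settled, and in which population it is analysed**

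| Endpoint | Settled | Main population | Reached by the exclusion? |
|---|---|---|---|
| EAD (5.1) | by day 7 | PP | yes |
| OCS liver assessment (5.2) | before transplant | PP | no, not a post-transplant assessment |
| Survival at discharge (5.2) | at discharge, possibly after day 7 | PP | yes |
| Survival at day 30 (5.2) | day 30 | PP | yes |
| Graft-related serious events (5.4) | day 30 | mITT | yes, but no PP analysis uses it |

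The OCS endpoint drops out because it asks whether "measurements of all of the following during perfusion will be available on OCS device before transplant". Among the secondary endpoints, only the two survival endpoints can trigger the exclusion.

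**Step 2: can EAD be known while later data are inadequate?** Yes. Section 8.2 makes collection of the EAD data at the set times mandatory, but asks only that the other follow-ups be attempted within 3 days either side. Under 5.1, EAD status is determined in two ways:
- positive, once any one criterion is met, for example AST above 2000 or primary non-function, even without day-7 laboratory values;
- negative, when AST is available through day 7, bilirubin and INR are available on day 7, and there is no primary non-function. Day-7 values alone do not settle a negative, because the AST criterion covers the whole week.

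Nothing in 10.2.1 says that a determined status is enough to keep the subject in PP.

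**Step 3: exclusion against imputation.** Take a subject with no day-7 INR and no other criterion met. If *adequate* is read strictly, the subject leaves PP, and imputation in PP has few or no subjects to act on. If it is read loosely, the subject stays and is imputed. In mITT the subject is imputed either way.

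**Step 4: size.** The plan gives no EAD rate and no exclusion count, so there is no figure to reproduce and the inputs below are assumptions. Let N = 184, x = EAD cases, k = excluded subjects with known status, and c = cases among them.

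PP rate = (x - c)/(N - k)

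Shift = (x - c)/(N - k) - x/N = [k/(N - k)] × (x/N - c/k)

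The shift is zero when the excluded subjects have the same EAD rate as everyone else. With x = 37, x/N = 37/184 = 20.11%:

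| k | c | PP rate | Shift (points) |
|---|---|---|---|
| 1 | 0 | 37/183 = 20.22% | +0.11 |
| 1 | 1 | 36/183 = 19.67% | -0.44 |
| 10 | 0 | 37/174 = 21.26% | +1.16 |
| 10 | 2 | 35/174 = 20.11% | 0.0 |
| 10 | 5 | 32/174 = 18.39% | -1.72 |
| 18 | 0 | 37/166 = 22.29% | +2.18 |
| 18 | 4 | 33/166 = 19.88% | -0.23 |
| 18 | 9 | 28/166 = 16.87% | -3.24 |

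Check of the last row by the second formula: (18/166) × (0.2011 - 0.5000) = -0.0324.

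The last row needs 9/37 = 24% of all EAD cases to be excluded for later data gaps.

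Other assumed base rates, with k = 18 and c = 0 or 9:
- 18/184 = 9.78% becomes 18/166 = 10.84% (+1.06) or 9/166 = 5.42% (-4.36).
- 55/184 = 29.89% becomes 55/166 = 33.13% (+3.24) or 46/166 = 27.71% (-2.18).

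As a yardstick, the exact 95% interval for 37/184 is 14.6% to 26.6%.

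**The case against.** The strongest reply is that the exclusion is narrower than it looks. It requires a failure to complete *adequate* assessments and sits in a list of *major* violations. Section 15.7 only has a missed or late assessment documented as a deviation. Few subjects may be affected, and a recipient known to have died before day 30 has known day-30 survival, so death itself is not a gap in that endpoint. The mITT analysis keeps everyone, section 10.3.2 already plans a listing of major deviations and counts by type, and the pending analysis plan could define the terms.

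Much of this stands. It limits the reach and means that a divergence would be visible. It does not remove the point: 10.2.1 states the *or* rule now, an analysis plan that kept these subjects would have to depart from it, and the headline analysis remains PP.

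A reader might also infer more than the documents support:
- *That the PP rate is biased in the device's favour.* Neither the number excluded nor their EAD rate is given; the shift can go either way or be near zero.
- *That exclusion and imputation contradict each other.* They can coexist: imputation works fully in mITT, and in PP on gaps not judged to be a failure.
- *That 10.3.4 contradicts the synopsis.* It rules out imputation for subgroups only, which is consistent with imputing in the main analysis.
- *That safety results are affected.* Safety is analysed in mITT.

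**Conclusion.** The point holds as a defect of definition. Read as written, the third PP exclusion can remove a subject with determined EAD status from the primary EAD analysis because secondary or safety assessments are inadequate, and its safety limb serves no stated PP analysis. Its primary-endpoint limb overlaps in PP with the planned imputation, with an undefined word as the only boundary.

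The size and direction of any effect are not established. If the excluded subjects resemble the rest, the shift is about 0.2 points or less in the 20% examples. A shift of a few points needs selective exclusion, and at the assumed 20% rate even the largest shift shown (to 16.9%) stays inside the 14.6% to 26.6% interval. These figures rest on assumed EAD rates of about 10%, 20% and 30% and at most 18 exclusions. The point merits correction because the selection has no analytic purpose and is cheap to remove.

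**What to change.** In 10.2.1:
1. Make the data-completeness exclusion endpoint-specific, so that inadequate data for one endpoint affect only that endpoint's PP analysis, and delete the reference to safety endpoints. Define *adequate* for each endpoint that remains.
2. State that no subject whose EAD status is determined is excluded from the primary EAD analysis for missing secondary or safety data. Determined means any EAD criterion met, or AST available through day 7, day-7 bilirubin and INR available, and no primary non-function.

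In 10.3.4:

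3. State that otherwise eligible PP subjects with missing EAD components are handled by the multiple imputation already planned in the synopsis.

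Removing the bullet altogether is not required. Reporting of exclusions by reason is mostly covered by 10.3.2; showing the counts beside the PP and mITT results would complete it.

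The cost is a few sentences before the analysis plan is finalized. The downside is that a few subjects with incomplete later data stay in PP, those with missing EAD components depend on an imputation model not yet specified, and the reported PP rate may move slightly either way.
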